7.2.5 Month 1 Visit

See Table 11 for the procedures and assessment to be performed for the Month 1 study visit. Outpatient visits should be completed as close to the scheduled visit dates as possible. There will be a window of +/- 1 weeks for the Month 1 study visits.

7.2.6 Month 3

See Table 11 for the procedures and assessment to be performed for month 3 study visit. Outpatient visits should be completed as close to the scheduled visit dates as possible. There will be a window of +/- 4 weeks for the Month 3 study visit.

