2.2 Study Endpoints

2.2.1 Primary Endpoints (Safety)

Safety will be assessed as the incidence within one month after an infusion of any treatment emergent serious adverse events (TE-SAEs), defined as one or more of the following events that: is life-threatening event (e.g., stroke or non-fatal pulmonary embolism); requires inpatient hospitalization or prolongation of existing hospitalization (e.g., for worsening dyspnea); results in persistent or significant disability/incapacity; results in death; or leads to clinically significant untoward laboratory test result(s) or medical condition(s), determined per Investigator' judgments.

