3. STUDY DESIGN

3.1 Description of the Study

A Pilot Phase will be performed to test the safety of dose and volume of cells administered via peripheral intravenous infusion. The first three (3) subjects in-group 1 (UCMSCs) will be treated first and safety will be fully assessed. Only if there is no evidence of treatment emergent SAEs in Group 1, treatment of subjects in Group 3 be undertaken.

The subjects in the high dose (Groups 3 & 4) will not be treated until the subjects in the low dose (Groups 1 & 2) have completed their one-month follow-up assessments and safety measures have been reviewed to confirm that there have been no treatment emergent SAE's. Treatment emergent SAE's, defined as the composite of: death, non-fatal pulmonary embolism, stroke, hospitalization for worsening dyspnea and clinically significant laboratory test abnormalities, prior to proceeding with the treatment of further subjects.

Subjects in each pilot phase group (Group 1, 2, 3 and 4) will not be treated less than 5 days apart.

Subjects in the pilot phase will receive a telephone call 5 days post infusion (+/- 1 day) to review adverse events.

The randomized portion of the study will be conducted after a full review of the safety data from the Pilot Phase by the DSMB.

Following the pilot study (12 subjects), thirty (30) subjects that meet inclusion criteria will be scheduled to undergo peripheral intravenous infusion.

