7. STUDY PROCEDURES

7.1. Time and Events Schedule

The Time and Events Schedule for the conduct of this study is shown in **Table 11**

Schedule of Assessments
Table 11: Time and Events Table

VISIT	Screening + 45 days	Baseline (0 to -4 weeks prior to Day 0)	Day 0	Week 2 (Day 14) ± 2 days	Month 1 (Day 30) ±1 weeks	Month 3 (Day 90) ±4 weeks	Month 6 (Day 180) ±6 weeks	Month 12 (Day 365) ±2 weeks
Informed Consent	X							
Full Medical History	X							
Physical Exam	X	X	X	X	X	X	X	X
Vital Signs ¹	X	X	X	X	X	X	X	X
12-lead (ECG)	X	X	X	X	X	X	X	X
Concomitant Medications	X	X	X	X	X	X	X	X
Randomization		X						
Infusion Treatment (IP)			X					
6 Minute Walk Test			X			X	X	
4 Meter Gait Speed Test			X			X	X	
QOL Questionnaires (EQ-5D, SF-36, IIEF (Male), SQOL-F(Female))		X			X	X	X	
Laboratory Testing ²								
Review Adverse Events		X	X	X	X	X	X	X
Brachial Ultrasound ³	X	X				X		
Dobutamine Stress Echo (DSE) ⁴	X						X	

Subjects in the pilot phase will receive a telephone call 5 days post infusion (+/- 1 day) to review adverse events

- 1- Weight, Height (will only be collected at screening)
- 2- See table 12 for specific tests done at each time point
- 3- Brachial ultrasound to assess endothelial function should be completed in the morning prior to 12p.m. Instruction for completing this assessment are outline in Appendix 3 of this protocol
- 4- Dobutamine Stress Echocardiogram (DSE) will be performed, at screening and at the Month 6 follow-up visit. Instructions for completing the (DSE) are outlined in Appendix 2 of this protocol. If the stress test needs to be stopped due to unforeseeable side effects and cannot be completed on a subject, this will not prevent them from being able to take part in the study.

Schedule of Laboratory Testing
Table 12: Time and Events Table

VISIT		SCR	BSL	DAY 0	W2	M 1	M 3	M 6	M 12
Standard Labs	CBC with Differential ¹	X		X	X	X	X	X	
	Comprehensive Metabolic Panel ²	X		X	X	X	X	X	
	PT, INR, PTT	X							
	Uric Acid, Pro BNP, hsCRP, IL6, Fib, D-dimer, TNFa,	X		X	X	X	X	X	
	Lipid Profile ³	X		X	X	X	X	X	
	Urinalysis	X		X		X	X	X	
	HbA1c	X				X	X	X	
	Pregnancy (childbearing women) ⁴	X		X					
Biomarkers / Immune	SST / PRA ⁵			X				X	
	MNCs ⁶			X	X	X	X	X	
EPCs	Endothelial Blood Samples ⁷		X				X		
Gene Expression	DNA ⁸			X					
	RNA			X				X	
Viral Serology	Infectious Disease Tests ⁹	X							

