9. The proportion of subjects experiencing TE-SAE as defined in Section 2.2.1 will be monitored within 30 days of infusion. This guideline is designed to assist the independent DSMB in overseeing the study and indicate boundaries needing discussion by the DSMB. The DSMB may also request additional interim analyses

and develop other criteria including provision for monitoring of potential late effects to determine when to intervene in the enrollment or treatment of subjects in the study.

10. Monitoring of key safety endpoints (refer to Table 8 in section 2.2.1) will be conducted.
11. The stopping guidelines serve as a mechanism for consultation with the DSMB for additional review, and are not formal “stopping rules” that would mandate automatic closure of study enrollment. It is designed to assist the independent DSMB in overseeing the study. The DSMB may also request additional interim analyses and develop other criteria including provision for monitoring of potential late effects to determine when to intervene in the enrollment or treatment of subjects in the study.
12. Study accrual and further treatment of subjects will be stopped if multiple (i.e. more than 1) subjects develop cardiorespiratory signs and symptoms that are persistent or lead to discontinuation of infusion.

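### The Month 1 visit may fall on Day 23, before the 30-day primary safety window ends, and the high-dose gate follows that visit rather than 30 elapsed days

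*Combined protocol and SAP*

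**What the plan says.** Section 2.2.1 defines the primary endpoint: "Safety will be assessed as the incidence within one month after an infusion of any treatment emergent serious adverse events (TE-SAEs". One component is laboratory-based: an event qualifies if it "leads to clinically significant untoward laboratory test result(s". Section 8.1.5, item 9, says that the proportion of subjects with such events "will be monitored within 30 days of infusion".

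Table 11 (section 7.1) lists the visit as "Month 1 (Day 30) ±1 weeks", and section 7.2.5 gives the same window: "There will be a window of +/- 1 weeks for the Month 1 study visits". The next visit is "Month 3 (Day 90) ±4 weeks". The laboratory schedule (Table 12 in section 7.1) has safety bloods at Week 2, Month 1 and Month 3, with none between Month 1 and Month 3. The only extra contact is a telephone call about 5 days after infusion, in the pilot phase.

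The synopsis and section 3.1 hold back the high-dose pilot groups until the low-dose subjects "have completed their one-month follow-up assessments and safety measures have been reviewed" and the review has found no treatment-emergent SAEs. Neither place states a minimum number of elapsed days. For the later step into the randomized phase, sections 9.3 and 9.4.3.3 do state one: pilot subjects must have been followed for 30 days.

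**The concern.** The endpoint and the visit that should close it do not have to end together. A subject seen on Day 23 is fully compliant, yet a week of the primary window still lies ahead, and nothing is scheduled in it. This matters most for the laboratory component, because a laboratory finding without symptoms exists only if blood is drawn. If the abnormality resolves before Month 3, no scheduled test will find it. If it is still present at Month 3, it will be found, but nobody can say whether it began inside the 30 days.

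The second consequence is for the low-dose review. That review looks for the absence of any treatment-emergent SAE in six subjects, so one late event would change its answer. Because the review is keyed to the visit, it can be signed off while some of those subjects are still inside their window. The protocol applies the 30-day standard explicitly at one gate and not at the other.

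**Working it through.** **Inputs**
- Endpoint window: one month (2.2.1) and 30 days (8.1.5, item 9). I treat these as the same, because Table 11 puts Month 1 at Day 30.
- Visit windows (Table 11): Week 2 = Day 14 ± 2; Month 1 = Day 30 ± 7; Month 3 = Day 90 ± 28.
- Spacing: at least 5 days between subjects within a pilot group (synopsis, 3.1).
- Low-dose subjects: 3 + 3 = 6.

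The plan gives no event rate or sample-size calculation, so the visit window is its only figure to check. Table 11 and section 7.2.5 agree on it.

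**Step 1: allowed days (nominal day ± window)**
- Week 2: 14 − 2 = 12 to 14 + 2 = 16
- Month 1: 30 − 7 = 23 to 30 + 7 = 37
- Month 3: 90 − 28 = 62 to 90 + 28 = 118

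**Step 2: part of the window after the earliest Month 1 visit**

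30 − 23 = 7 days; 7/30 = 23.3% for that subject. With a visit on the nominal Day 30 it is zero.

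**Step 3: time from a Day 23 draw to the next scheduled draw**

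62 − 23 = 39 days at the earliest, 90 − 23 = 67 at the nominal day, and 118 − 23 = 95 at the latest.

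**Step 4: open windows at the earliest low-to-high-dose gate**

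Assume minimum spacing, every low-dose subject seen on Day 23, and the review done on the day of the last visit.
- Groups 1 and 2 treated in parallel: when the last subjects reach Day 23, each group stands at Days 33, 28 and 23. The shortfall is 0 + 2 + 7 = 9 days per group, 18 in all. 18/(6 × 30) = 10%, in 4 of 6 subjects.
- Five-day spacing across all six: Days 48, 43, 38, 33, 28 and 23. The shortfall is 2 + 7 = 9 days. 9/180 = 5%, in 2 of 6 subjects. The result is the same if Group 1 finishes its month before Group 2 starts.

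Each day that the review takes shortens these gaps. A review lasting 2 days closes the 2-day shortfalls, and one lasting 7 days closes them all.

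**Step 5: illustration with assumed risks**

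Let p be a subject's 30-day risk of a treatment-emergent SAE, with onset uniform over the 30 days and subjects independent. With m days still open for each subject, the chance of at least one in-window event after the gate is 1 − ∏(1 − p·m/30). For p = 10% in the parallel case:

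1 − (1 − 0.10 × 7/30)² × (1 − 0.10 × 2/30)² = 1 − 0.9539 × 0.9867 = 5.9%.

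| Assumed p | Parallel groups | Spaced across all six |
|---|---|---|
| 2% | 1.2% | 0.6% |
| 5% | 3.0% | 1.5% |
| 10% | 5.9% | 3.0% |
| 20% | 11.5% | 5.9% |

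These percentages rest entirely on assumed values of p. They show scale and are not estimates.

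**The case against.** A reader might infer that late-window laboratory events cannot be seen at all. The documents do not support that. Section 8.14 has all AEs collected whenever they occur during the trial, and section 8.12 requires SAEs to be recorded within 24 or 48 hours of the investigator becoming aware of them. A symptomatic event or an outside test on Days 24 to 30 can therefore be captured, and a persistent abnormality would appear at Month 3. What escapes scheduled detection is the silent, transient abnormality, plus the onset date of a persistent one.

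Nor should the 7 of 30 days be read as if the other 23 were fully observed. Bloods are drawn at Week 2 and Month 1 only, so a silent, transient abnormality on Day 20 could be missed even with a visit on Day 30. This objection stands. The visit window adds to a sparse schedule and is not the sole cause of the gap.

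A reader might also infer that the randomized phase could start on short follow-up. It could not: sections 9.3 and 9.4.3.3 require 30 days, although the last scheduled draw behind that review may still be from Day 23.

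There are other safeguards. Section 7.2.5 asks for visits as close to schedule as possible, so Day 23 is the extreme and not the plan. The 5-day spacing prevents all six low-dose subjects from being short of Day 30 together. The DSMB Chair is told of every SAE (9.3), and certain serious events within 30 days put accrual on hold (8.1.5), so a recognised late event can still act after the gate.

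These points limit the size of the problem. They do not remove the mismatch, because continuous AE collection schedules neither a contact nor a blood draw, and a Day 23 visit satisfies the protocol.

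**Conclusion.** The point holds as a mismatch that the windows permit, not as a loss that is certain to occur. Followed as written, the plan can complete the assessment of its primary endpoint up to 7 days before the window ends for a given subject, with no scheduled contact or draw for the next 39 to 95 days. At the earliest gate, 2 to 4 of the 6 low-dose subjects, or 5 to 10% of low-dose subject-days, could still be inside the window. That range assumes minimum spacing, Day 23 visits throughout and a same-day review, so it is a ceiling for each treatment order considered. The 23% figure is one subject's worst case and should not be read as the share of endpoint information lost.

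Two documented standards, completed one-month assessments and 30 days of follow-up, govern two gates that rest on the same endpoint. These passages must be reconciled. This is a cheap improvement of minor to moderate severity, worth making because safety is the trial's primary question.

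**What to change.** - In Table 11 and section 7.2.5, align the Month 1 window with the endpoint so that the assessment closing the window does not precede Day 30. Day 30 to Day 37 is one example.
- In section 2.2.1, use one expression for the window in place of both one month and 30 days, and count treatment-emergent SAEs by onset date, Day 0 to Day 30.
- State how a laboratory abnormality first found after Day 30 is classified. With a later visit, an abnormality found on, say, Day 37 has no known onset, so a convention is needed in advance.
- Reconcile the high-dose gate wording in the synopsis and section 3.1 with the 30-day follow-up wording in sections 9.3 and 9.4.3.3. Which standard applies is for the sponsor and the DSMB to decide.

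The cost is a few wording edits. The pilot review may come up to a week later, and some laboratory findings made after Day 30 will have uncertain onset whichever convention is chosen. The change does not fill the gap between the Week 2 and Month 1 draws.

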7.2.7 Month 6 - Month 12 Visit (Final Study Visit)

See Table 11 for the procedures and assessments to be performed for Month 6 through month 12 visit of the study. Outpatient visits should be completed as close to the scheduled visit dates as possible. There will be a window of ± 6 weeks for the Month 6, and ± 2 weeks for the Month 12 study visits.

7.3 Assessment Details

7.3.1 Physical Exam

A complete medical history will be conducted during screening testing including: vital signs, height and weight; medical, surgical, and smoking history; and review of current use of prescription and OTC medications. Similar physical exams will be conducted at each additional clinic visit during the study including vital signs, weight, review of AEs, and concomitant medications.

7.3.2 Vital Signs

Vital sign measurements will be performed at least once on each study visit up to time of discharge. These measurements will consist of oxygen saturation, weight, respiratory rate, heart rate, blood pressure, and temperature. Respiratory rate, heart rate, and blood pressure should be measured in a sitting position after 5 minutes of rest. Height will only be collected at the screening visit.

7.3.3 Dobutamine Stress Echocardiography (DSE)

A Dobutamine Stress Echocardiography will be performed twice during the study, once at screening and at the Month 6 follow-up visit. This exam will assist in mimicking the effect of exercise on subjects to assess the heart muscle and ejection fraction when under stress. (refer to appendix 2)

7.3.4 Flow Mediated Diameter percent change (FMD%)

A Flow Mediated Diameter percent change will be performed three times during the study, once at screening, baseline, and at the Month 6 follow-up visit. This exam will assess vascular function. All measurements of the brachial artery diameter and FMD will be performed in the morning, in a quiet and dark room. (refer to appendix 3)

7.3.5 Laboratory Testing

- Gene Expression**

A separate blood sample of approximately 17mL for gene expression (DNA) profiling of WBC (at Day 0 visit) and A separate blood sample of approximately 5.0mL for RNA expression analysis (at Day 0 and month 6 visits) will be obtained from the study participants, as detailed on Table 12. A separate genetic consent form is completed by the study participants.

All samples will be identified so that they can be linked to individual subjects. These samples may be stored indefinitely. Individual results will not be returned to the subject or the study physician. The samples will be linked to subjects, but there will be no recontact. Data presented in publications will not contain individual subjects' clinical characteristics or outcomes; only aggregate data from the entire study will be disclosed.

- Biomarkers/Immune**

The studies planned in this protocol will utilize allogeneic hBMMSCs or hUCMSCs in subjects with chronic inflammation due to the metabolic syndrome. The use of an allogeneic graft raises the potential of graft rejection through immune cells resulting in failure of the therapy. hBMMSCs or hUCMSCs are ideal candidates for allogeneic transplantation because they show minimal MHC class II and ICAM expression and lack B-7 co-stimulatory molecules necessary for T-cell mediated immune responses^{57,58}. Indeed both types of cells do not stimulate a proliferative response from alloreactive T-cells even when the cells have differentiated into other lineages or are exposed to proinflammatory cytokines. Previous studies have demonstrated that MSCs have significant immunomodulatory effects, inhibiting T-cell proliferation, prolonging skin allograft survival, and decreasing graft-versus-host disease (GVHD). Recently human MSCs were shown to alter the cytokine secretion profile of dendritic cells, T cells, and natural killer cells in vitro, inhibiting secretion of proinflammatory cytokines (e.g. TNF α , IFN- γ) and increasing expression of suppressive cytokines (e.g. IL-10), possibly via a prostaglandin E2 mediated pathway.

In vivo studies of the fate of MSCs have shown that, when transplanted into fetal sheep, human MSCs engraft, undergo site-specific differentiation into various cell types, including myocytes and cardiomyocytes, and persist in multiple tissues for as long as 13 months after transplantation in non-immunosuppressed immunocompetent hosts. Further, in vivo studies using rodents, dogs, goats, and baboons demonstrate that allogeneic MSCs can be engrafted into these species without stimulating systemic alloantibody production or eliciting a proliferative response from recipient lymphocytes. These findings, coupled with our demonstration of efficacy of these cells for cardiac repair, solidify the notion of using MSCs as an allograft for successful tissue regeneration.

As part of the CERES protocol we will obtain peripheral blood samples from all subjects to evaluate the presence of activated T cells. Two heparinized (green top) vacutainer tubes (approx. 15 cc total blood) will be collected at different time points during the study (Reference Table 12 for schedule). Peripheral blood mononuclear cells (PBMC) will be isolated from heparinized blood by ficoll sedimentation and will be viably cryopreserved for planned assessments of T cell activation.

Two of the best-accepted markers of T cell activation are CD69 and CD25 (IL-2 receptor). We will monitor the activation of T cells by flow cytometric analysis of CD3+CD25+CD69+ cells in thawed PBMC. CD69 is an immediate/early marker of CD3+ T cell activation while CD25 expression increases within 1-2 days of activation and remains sustained over the intermediate-long term during chronic immune activation. Given the differences in the kinetics of CD69 and CD25 up regulation, assessment of both activation phenotypes (CD3+CD69+ and CD3+CD25+) will maximize the sensitivity of detection of T cell activation following allogeneic MSC infusion.

Additionally, in female subjects who receive allogeneic hBMSCs or hUCMSCs, the stored baseline serum will be analyzed to evaluate the antibody responses to HLA and H-Y antigens.

These samples will 1) provide storage of critical biomaterials derived from subjects enrolled in CERES 2) provide long-term integrity of these biospecimens and samples, and 3) provide management of samples for postdoctoral studies of immunologic, immunohistochemical, cellular, and molecular analyses of collected samples; as well as cell-surface markers (CXCR4, C-Kit, & Connexin 43), transcriptomic/Proteome (DNA, RNA, miRNA, protein samples, and telomerase, akt), growth factors (Sdf-1, notch,), functional Assays (cell growth rate, VEGF, and CFU assay), CD3, CD25, CD69, Inflammatory (IL-1, TGF-) , (but not limited to these biospecimens) will be used for research purposes only, will be stored without personal identifying information, and will be shared with approved researchers who will conduct studies to improve the understanding of the effects of cell therapies and/or of metabolic syndrome.

- **EPCs**

Blood collection will be performed to assess endothelial function in the metabolic syndrome population at baseline and 3 months post stem cell infusion. This will

help provide cumulative data in assessing whether or not stem cell infusion improves endothelial function.

Assay of colony forming units: Fresh blood will be processed for cell culture assays for endothelial progenitor stem cells colonies counting (a 5 days' protocol). Fifty milliliter of blood will be processed; peripheral-blood mononuclear cells will be isolated by Ficoll density-gradient centrifugation, will be washed twice in phosphate buffered saline with 5% fetal bovine serum and re-suspended in media (EndoCult basal media with supplements; StemCell Technologies, Vancouver, British Columbia, Canada) for EPC colony-forming assay. Cells will be planted on human fibronectin-coated plates (BIOCOAT; Becton Dickenson Labware, Bedford, Massachusetts) at a density of 5X10⁶ cells/well and incubated at 37°C in humidified 5% CO₂. After 48 hours, the non-adherent cells will be re-plated onto fibronectin-coated 24 well plates at a density of 1X10⁶ cells/well. After 5 days, colony forming units (defined as a central core of rounded cells surrounded by elongated and spindle-shaped cells) will be counted manually in 8 wells out of a 24-well plate.

8. SAFETY

8.1 Safety Variables

1. Vital signs
2. Physical examination
3. Clinical laboratory tests
4. Adverse events

8.1.1 Laboratory Evaluations

At screening, the HIV-1 and HIV-2 tests, Syphilis – VDRL (If VDRL is reactive Confirmation with FTA-ABS is needed), CMV, hepatitis screen and β -HCG serum pregnancy tests (only for women of childbearing potential) will be performed locally at the study site. Laboratory safety tests will consist of the following:

Serum chemistry: sodium, potassium, chloride, BUN, creatinine, glucose, calcium, AST/SGOT, ALT/SGPT, carbon dioxide, total bilirubin (fractionate if total >1.5 times normal), alkaline phosphatase, albumin, fibrinogen, IL6, D-Dimer, Coagulation studies

Hematology: hemoglobin, hematocrit, platelets, WBC, RBC,

The Investigator will review all clinically relevant laboratory results requested in the protocol. The diagnosis associated with any clinically significant laboratory deviations should be recorded as an AE and should indicate the underlying abnormality or diagnosis (such as renal insufficiency) as opposed to the observed deviation in laboratory results (such as elevated creatinine). If there is no underlying abnormality linked to a clinically significant abnormal laboratory value, the observed deviation should be reported as the AE.

